## 5.0 STUDY DESIGN AND METHODS

### 5.1 Design/Study Type

#### 5.11 First Phase:

Ten patients will be purposively sampled to enroll a diverse group based upon guidelines for the Phase Ia and Ib of the Obesity-Related Behavioral Intervention Trials (ORBIT) model for behavioral treatment development (Figure 2). In the first phase, we will enroll at least 3 patients who are  $\geq 65$  years of age, 3 patients from racial/ethnic minority groups, and 2 patients who do not use text messages to communicate  $>1x/week$  based upon evidence that patients with computer experience are more receptive to electronic self-reporting than those without experience.

**Figure 2**

We anticipate enrolling 10 patients to refine the HOPE App intervention and determine which accelerometer (Fitbit Zip and Fitbit Charge 2) will be used in phase II of the study. In this phase of the study all participants will receive the smartphone app, the Fitbit Zip, and the Fitbit Charge 2 so that we can: 1) identify which wearable accelerometer to use in the second phase, and 2) compare step counts between the accelerometers (the smartphone, a hip-worn device, and a device worn on the non-dominant arm).

### 5.12 Second Phase

A feasibility and acceptability study will employ convenience sampling from 100 consecutive patients who meet inclusion criteria in a pilot randomized trial of:

- Arm 1: Fitbit + active app
- Arm 2: Fitbit + passive app
- Arm 3: Active app
- Arm 4: Passive app

There are two versions of the HOPE smartphone app—“active” and “passive.” The “active” smartphone app refers to the version of the smartphone app in which active symptom collection is occurring (e.g., patients are receiving surveys and receiving tailored symptom management advice) in addition to passive data collection (accelerometer, GPS, Incoming calls and texts, etc.) The “passive” smartphone app refers to the version of the smartphone app in which only passive data collection is occurring, and no surveys or active data collection are being sent to participants. In the passive app, participant interaction with the smartphone app consists of installing the app and keeping it running in the background of their phone; all data is collected in the background. The active and passive apps are built on the same underlying platform and the security protections for the active and passive smartphone apps are identical, detailed in Appendix L, HOPE App Data Privacy and Security.

All patients will be assigned to a separate, secondary randomization either to be encouraged to wear their smartphone on them at all times, or not to be encouraged to wear their smartphone at all times (refer to study schema for details.) We have no reason to believe that encouragement to wear a smartphone will impact patients’ health-related quality of life, performance status, and use of high-intensity health care/phone calls; thus, the secondary randomization will not impact the comparison of the 4 study arms for these outcomes.

With a total sample size of 100 patients (25 patients per arm), this study design will yield 70% power to detect a 6-point change in EQ-5D and 80% power to detect a 7-point change in patients’ health-related quality of life (measured with the EQ-5D; see section 6.0). Our analyses will also provide preliminary estimates of feasibility, acceptability, safety outcomes, scale scores, missing data, and participant and physician feedback.

## **5.2 Selection of Instruments**

### 5.21 Interviews and Surveys

The following measures will be used in the study interviews and surveys, including the *Participant Baseline Interview* (Appendix C), *Participant Post-Baseline Interview* (Appendix D), *Clinician Survey* (Appendix E), and *Symptom Survey* (Appendix F). Table 1 outlines their distribution across the study instruments.

#### **5.21a Global Health Status: EQ-5D-5L**

The EQ-5D is a standardized measurement of health status that has been used in a wide range of health conditions and treatments, including cancer patient populations. The EQ-5D-5L is the most recent 5-level version that has proven validity and reliability in a range of patient groups with chronic diseases and cancer. It is a 5-item questionnaire (measuring mobility, self-care, usual activities,

pain/discomfort, and anxiety/depression. Each dimension has three levels of perceived problems: 1) no problems, 2) slight problems, 3) moderate problems 4) severe problems, and 5) extreme problems. Patients check the statement level that best describes their current health status in each dimension, which are then scored to generate a patient's unique health state. In the EQ-VAS, patients report a single index value of how good or bad their current health state is on a visual scale that ranges from worst imaginable at zero to best imaginable at one hundred. The EQ-5D-5L can be administered with little to no guidance and takes only a few minutes to complete. Upon scoring, the EQ-5D produces a composite score between 0-1 (multiplied by 100 to generate a number between 0-100), which represents general health status, normalized for the US population. Lower scores represent worse quality of life, and a change of  $\geq 6$  is clinically significant in US cancer populations.

### **5.21b PROMIS Global-10 and PROMIS Physical Function short form 6b**

The PROMIS Global-10 is a brief measure of patient health status that is not disease specific. It consists of 10 questions; e.g. "In general, how would you rate your physical health?" Items are scored on a Likert scale of 1-5, where higher scores indicate better health, except for pain which is measured on a 10 point scale. Standardized T-scores (range 0-100) are calculated for the global physical and mental health scales, and higher scores indicate better health. The full scale takes approximately 2-3 minutes to complete and will be used at baseline, post-baseline survey and the single-item global quality of life and physical health questions will be used daily among those randomized to the smartphone app.

The PROMIS Physical function (PF) 6b is a brief, 6 item measure used to characterize patients' overall health, level of physical disability, and general well-being. The PROMIS PF 6b has been validated in 4,840 cancer patients across a range of ages, racial/ethnicity groups, stages and cancer types, and normalized for the US population. It has high reliability, minimal floor effects, and can precisely measure meaningful differences in functional status, disease burden, and comorbidities.

### **5.21c Performance Status: ECOG PS**

The Eastern Cooperative Oncology Group (ECOG) Performance Status (PS) assessment is a standard measurement that oncologists often use to assess a patient's current functional level and eligibility for clinical trials. The scale ranges from 0 to 5 and the criteria for each grade is as follows: 0 = Fully active, able to carry on all pre-disease performance without restriction; 1 = Restricted in physically strenuous activity but ambulatory and able to carry out work of a light or sedentary nature, e.g., light house work, office work; 2 = Ambulatory and capable of all self-care but unable to carry out any work activities; up and about more than 50% of waking hours; 3 = Capable of only limited self-care; confined to bed or chair more than 50% of waking hours; 4 = Completely disabled; cannot carry on any self-care; totally confined to bed or chair; 5 = Dead.

The ECOG PS will allow clinicians and participants to provide a standard evaluation of the participant's performance status over time and with minimal burden. Participants will use the patient self-report version that has been used successfully in a study with cancer patients. We expect that it will take 1-2 minutes to answer the question.

### **5.21d Depression: PHQ-9**

The Patient Health Questionnaire-9 (PHQ-9) is a validated self-report measure that assesses nine depressive symptoms using Diagnostic and Statistical Manual of Mental Disorders, Fourth Edition (DSM-IV) diagnostic criteria for major depressive disorder. It is used to screen, diagnose, and monitor depressive symptoms and has been administered/demonstrated validity in cancer patients, as well as smartphone apps. Respondents report if each symptom has bothered them "not at all," "several

days," "more than half the days," or "nearly every day" during the previous two weeks. We expect that it will take participants no more than 3-5 minutes to complete.

### **5.21e Symptoms Assessment: CTCAE and PRO-CTCAE**

The Patient-Reported Outcomes Version of the Common Terminology Criteria for Adverse Events (PRO-CTCAE) is a patient-centered, standardized self-report measure that enables patients to report symptoms and AEs. Clinicians will use the standard CTCAE items (used to rate and report toxicities in therapeutic drug trials) while participants will use the PRO-CTCAE items. [name], one of the study's investigators, was one of the first researchers to identify, develop, test, refine and validate methods for collecting PROs. She was instrumental in the development of the primary study measure, the PRO-CTCAE, which demonstrated favorable validity, reliability, and responsiveness in a large heterogeneous United States sample of cancer patients undergoing treatment. Ten PRO-CTCAE items that are salient to gynecologic cancers will be collected, including: abdominal pain, nausea, vomiting, constipation, diarrhea, peripheral neuropathy, anxiety, depression, dizziness and fatigue.

The PRO-CTCAE items use conditional branching for AEs that contain multiple attributes. For example, if a participant reports a symptom, she is asked to quantify the severity and the extent to which the symptom interfered with her daily activities; if she does not report a symptom, these items are skipped. We anticipate that participants and oncology providers will complete their respective versions of the measure in about 3-5 minutes. Participants enrolled in phase I, and intervention arms 3 and 4 in the second phase RCT will also report their symptoms weekly in the HOPE app intervention.

### **5.21f Anxiety: GAD-7**

The Generalized Anxiety Disorder 7-Item (GAD-7) is a reliable and validated self-report measure that assesses GAD. Respondents rate how often they have been bothered by 7 anxiety symptoms over the past two weeks using the following scale: 0 = Not at all; 1 = Several Days; 2 = Over half the days; and 3 = Nearly every day. Respondents also answer a question to assess the duration of their anxiety symptoms. Responses are tallied and the total score indicates the presence and severity of GAD.

The measure has since been validated in the general population and was the recommended evaluative measure for anxiety in adult cancer patients in the 2014 American Society of Clinical Oncology (ASCO) Guideline Adaptation. We anticipate that it will take participants approximately 3-5 minutes to complete.

### **5.21j Overall Quality of Life and Physical Health: FACIT-PAL**

Patients' quality of life (QoL) will be assessed with Functional Assessment of Chronic Illness Therapy – Palliative Care, which has demonstrated internal consistency, reliability and validity. The measure is divided into four primary QoL domains: physical well-being (7-items), social/family well-being (7-items), emotional well-being (6-items), and functional well-being (7-items). It also includes 12 additional items that are specific to palliative care priorities for patients with chronic illnesses such as cancer. Participants will rate each symptom over the past 7 days as: 0) Not at all; 1) A little bit; 2) Somewhat, 3) Quite a bit, and 4) Very much. Subscales can be analyzed separately or aggregated to produce a total score.

### **5.21k Literacy Measures: Health Literacy and Numeracy & Mobile Communication Competence**

Health literacy and numeracy and mobile communication competence will be collected for all participants at baseline. The "comfort with technology" and "mobile preference" subscales of the Mobile Communication Competence scale will be used because they assess factors directly impacting patients in our study, who will be asked to acclimate to and consistently use an accelerometer and/or

smartphone app. The mobile communication preference and comfort with technology subscales individually demonstrated internal reliability, consistency and validity. We estimate that it will take participants approximately 5 minutes to complete all of the literacy measures.

### **5.21l Demographic Information**

Basic demographic information will be collected for all participants, including: age, marital status, race/ethnicity, education, household structure, income, and employment. The questions will only take a few minutes to complete.

### **5.21m Smartphone Usage Questions**

Data on smartphone-specific usage habits will be collected for all participants. Participants will be asked a total of four questions: average daily time spent using smartphone, purpose of using smartphone, comfort using smartphone apps, and frequency of using smartphone apps. We estimate that it will take participants approximately 2 minutes to complete these questions.

### **5.21n Cancer Experience Question**

#### *About the cancer experience question*

On a weekly basis, participants will be asked one qualitative question about their cancer experience. We hope that this open-ended question will give patients an opportunity within the study to express additional concerns, emotions and experiences regarding their cancer that may not be adequately reflected in other study instruments. A large body of previous work has successfully asked cancer patients to share open-ended, qualitative measures of their emotional experiences (i.e. by writing in response to a prompt). However, to our knowledge, our study will be the first to examine whether these qualitative measures correspond with clinical outcomes measured in real time in the real world.

Using a question adapted from Stanton and colleagues' emotional expression study with breast cancer survivors, participants will be asked to describe their experience with cancer over the course of the previous week. Participants will be presented with the cancer experience question as an audio survey within the HOPE App once a week (see Appendix F for question text) and will record their answers into the microphone of their smartphone. The app reminds the participant to make a voice recording in the same way that it reminds the participant to take any other survey in the HOPE app: by making a notification appear in the phone. The participant does not need to make a voice recording immediately and may wait until she is in private to do so. The participant can make the audio recording in the app at any time after the notification appears, until the next audio recording reminder replaces it. Participants will spend up to 5 minutes on this question, depending on how much they wish to share. This question will be answered within the smartphone app at the baseline interview and symptom survey (once weekly).

#### *Audio recording data security*

Patients will be informed about the audio recording questions in the study in the consent form and during the informed consent process and will be encouraged to ask any questions they may have about the audio recording.

In the weekly audio recording questions, the participant's voice is recorded as an MP4 audio file so that researchers can analyze the audio file. The app's voice recording feature does not ask for any identifiable information, but it is conceivable that, in the course of describing his/her day, a participant

could speak his/her own name or reveal other identifying details. As such, the voice recording data is encrypted.

For all data except voice recording data, the app encrypts the data line-by-line as it writes data to the device's disk. This means that the app never writes unencrypted data to disk for these files. For the voice recording file, it is not feasible to do on-the-fly asymmetric encryption (since most of the established stream ciphers use symmetric encryption), so the voice recording file is encrypted once the recording is complete. Because the phone cannot decrypt any of its own data, when the participant views his/her survey answers, the participant is actually logging in to the server, downloading the answers via an SSL connection, and effectively viewing them through an HTTPS site, not decrypting any data on the phone.

The HOPE App will employ the same data privacy and security processes used in six IRB approved protocols across three Partners Institutions (BIDMC Protocol #: 2015P-000240; McLean Hospital Protocol #: 2015P001303, 2015P001538, 2012P000890, 2015P002189; MGH Protocol #: 2015P000666). This list includes IRB-approved research studies that have also used the voice recording component of the app with patients as research participants. Although the app collects a large amount of data, it was custom built to be used in a health care setting and includes robust security and privacy features to safeguard all data and protect participants' privacy, including data anonymity, participant authentication, and data encryption.

Recordings will be tied only to a study ID number, and the only document linking the patient's study ID to identifiable information is in a restricted-access, password-protected file stored securely on Dana-Farber servers. Audio recordings from the HOPE App will be transcribed for further analysis using a DFCI-approved, HIPAA-compliant transcription vendor. All patient identifiable information will be removed when the audio recordings are transcribed. Audio recordings will be destroyed when analyses are complete.

#### *Cancer experience question analysis plan*

We plan to analyze qualitative data from the cancer experience question using the Linguistic Inquiry and Word Count (LIWC) program, developed by James Pennebaker and colleagues and used widely in emotional expression literature with cancer patients and other populations. LIWC reads text and identifies which words are associated with psychologically-relevant categories, i.e. affect, cognitive processes, content dimensions, etc. Because the holistic nature of the responses may not be adequately captured by the word count approach of LIWC analyses, we also plan to perform a content analysis of the output from the cancer experience question with trained independent raters, examining categories of psychologically relevant content in the recordings. For Phase I, due to the limited sample size, analyses will be descriptive in nature. For Phase II, we plan to use multivariate analyses of covariance (MANCOVA) as primary statistical procedures, controlling for baseline values, on conceptually related groups of variables including physical health-related outcomes (i.e., symptoms and healthcare utilization), psychological adjustment as measured by other study instruments (i.e., quality of life and emotional acceptance), and psychological properties of participants' responses to the cancer experience question (i.e. positive and negative affect). We also plan to conduct preliminary multivariate analyses of variance for continuous variables and chi-squared analyses for categorical variables, on demographic variables, cancer-related parameters, and other relevant variables (e.g. quality of life) at baseline. If relevant, we will use the baseline values on these measures as covariates to control for nonsignificant chance variation between groups at baseline.

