### **5.21o Brief COPE**

The Brief COPE is a 28-item measure developed to assess a broad range of coping responses. The Brief COPE has been validated in several populations including breast cancer patients and community samples. Subscales of the Brief COPE include use of emotional support, religion, and self-distraction, and individual subscales can be used independently. We will use the denial, behavioral disengagement, self-distraction, active coping, use of emotional support, use of instrumental support, positive reframing, planning, acceptance, and religion subscales of the Brief COPE. The Brief COPE will be administered to patients during the participant baseline interview (Appendix C).

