**Table 3. Second phase RCT instrument data collection per study arm**

INSTRUMENT		DAY						
		Visit 0	1-29	Visit 30	31-89	Visit 90	91-179	Visit 180
	Participant Baseline Interview	1,2,3,4						
	Participant Post-Baseline Interview			1,2,3,4		1,2,3,4		1,2,3,4
	Clinician Survey	1,2,3,4		1,2,3,4		1,2,3,4		1,2,3,4
	Health/Tx Info	1,2,3,4		1,2,3,4		1,2,3,4		1,2,3,4
	Healthcare Utilization			1,2,3,4		1,2,3,4		1,2,3,4
	Call Log			1,2,3,4		1,2,3,4		1,2,3,4
	Accelerometer Data		1,2	1,2	1,2	1,2	1,2	1,2
	Daily Quality of Life, Physical Function, and Symptom Questions		1,3	1,3	1,3	1,3	1,3	1,3
	Weekly Cancer Experience Question	1,3	1,3		1,3		1,3	
	Weekly Physical Function Survey		1,3	1,3	1,3	1,3	1,3	1,3

1. Fitbit + active app

2. Fitbit + passive app

3. Active app

4. Passive app

Data obtained via interviews, surveys and chart abstractions will be stored on the Harvard REDCap server. HOPE App will employ the same data privacy and security processes used in six IRB approved protocols across three Partners Institutions (BIDMC Protocol #: 2015P-000240; McLean Hospital Protocol #: 2015P001303, 2015P001538, 2012P000890, 2015P002189; MGH Protocol #: 2015P000666). Although the app collects a large amount of data, it was custom built to be used in a health care setting and includes robust security and privacy features to safeguard all data and protect participants' privacy, including data anonymity, participant authentication, and data encryption. Hope App Data Privacy and Security describes the processes in detail.

Fitbit data will be stored with Fitabase, a research platform that collects and stores data from Internet connected devices, like Fitbit, for monitoring and analysis. It provides minute-by-minute measures (e.g. steps, heart rate) for data monitoring and analysis. All data will be anonymized with the use of participant codes, and the data will be stored a in high security data center.

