For the primary analysis, the EQ-5D index scores will be calculated in each study arm at both baseline and 6 months and compared. The effect of the Fitbit on EQ-5D will be obtained by comparing the mean change in EQ-5D among all arms that consist of the Fitbit (i.e. arms 1 and 2) versus that obtained among all arms that do not consist of the Fitbit (i.e. arms 3 and 4). Similarly, the effect of the HOPE app on EQ-5D will be obtained by comparing the mean change in EQ-5D among all arms that consist of the HOPE app (i.e. arms 1 and 3) versus that obtained among all arms that do not consist of the HOPE app (i.e. arms 2 and 4). Additionally, pair-wise comparisons will be conducted of arms 2, 3, and 4 to arm 1 to examine which arms are driving or diluting any differences observed. Mean score changes from baseline will be compared using t tests and multivariable linear regression. The multivariable linear regression model will consist of change score as the dependent variable, and will adjust for baseline covariates (age, sex, cancer type, race, education, and literacy and numeracy). Additional analyses will use Fisher's exact test to compare the proportion of patients in each study arm who experience an improvement, no change, or a decrement in quality of life. This will be conducted both for any level of change from baseline and for a 6-point change from baseline (the threshold for a clinically meaningful difference). Similar analyses will be conducted for the secondary outcomes, including anxiety, depression, and number of patient phone calls, using the appropriate regression model (e.g. negative binomial regression may be used for the outcome of the number of patient phone calls).

For the health care utilization endpoints of unplanned infusion appointments, emergency room visits, and hospitalizations, cumulative incidence functions will be calculated with death treated as a competing event. Competing risk regressions will be used to model risk with and without adjustment for baseline covariates.

Agreement between patient-oncologist estimates of performance status will be estimated by Cohen's Kappa statistic, and differences in agreement between the study groups will be tested by bootstrapping.

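### The Phase 2 MANCOVA plan for the cancer experience recordings contains no model linking recordings to clinical outcomes, and it lists as an outcome emotional acceptance, for which only a baseline measure is described

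*Combined protocol and SAP*

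**What the plan says.** All references are to Part 1 (HOPE Trial), Phase 2.

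- **Purpose.** Section 5.21n says the study will "examine whether these qualitative measures correspond with clinical outcomes measured in real time".
- **Method.** The analysis plan in the same section names "multivariate analyses of covariance (MANCOVA) as primary statistical procedures, controlling for baseline values, on conceptually related groups of variables". It does not name the between-group factor.
- **Outcome sets.** There are three: "physical health-related outcomes (i.e., symptoms and healthcare utilization"; "psychological adjustment as measured by other study instruments (i.e., quality of life and emotional acceptance"; and the psychological content of the recordings, meaning positive and negative affect.
- **Acceptance.** Section 5.21o lists acceptance among the Brief COPE subscales and says: "The Brief COPE will be administered to patients during the participant baseline interview (Appendix C".
- **Recordings.** In Table 3 the row "Weekly Cancer Experience Question" is filled for arms 1 and 3 only, at Visit 0 and between visits. Sections 5.12 and 5.32a agree that the passive app sends no surveys.
- **Utilization.** Table 3 places it at Visits 30, 90 and 180. The chart-abstraction procedure in 5.5.1 has the form completed at the baseline visit as well. Section 5.22b describes the data as covering the enrollment period.

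**The concern.** A MANCOVA compares groups on several outcomes at once. With recording affect in one outcome set and the clinical variables in the others, each set is compared between groups and nothing estimates how affect in a recording goes with symptoms or quality of life. That association is the stated reason for asking the question.

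Two inputs also look unsupported. An outcome adjusted for its baseline needs a baseline and a later value, yet the described acceptance measure is taken once. Utilization needs a baseline value, and the protocol does not say what that value would cover.

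Patients in arms 1 and 3 are asked for up to five minutes of recording each week, and the audio is later transcribed, rated and destroyed. If the linking analysis is not written down, the choice of word-count category, outcome and time window falls to whoever analyses the data after seeing them. The trial's EQ-5D conclusion is not at stake.

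**Working it through.** **1. Sample-size inputs.** The plan gives no power or effect size for the MANCOVA, so there is no figure to reproduce on this point. As a check on the group sizes, the EQ-5D table in 6.2 was recomputed with 50 v 50 per factor, SD 14 and one-sided 5%. The standard error is 14 × √(2/50) = 2.8.

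- 6 points: Φ(6/2.8 − 1.645) = 69.1% (stated 70%).
- 7 points: Φ(7/2.8 − 1.645) = 80.4% (stated 80%).

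So 25 per arm is confirmed, and arms 1 and 3 hold 25 + 25 = 50 patients.

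**2. Is there a linking model?** The plan in 5.21n has none: recordings and clinical measures are both outcomes. Section 6.4 adds no analysis of the recordings. Section 2.2 also has a week-level hypothesis (more negative affect before scans, moderated by coping style), and 5.21n specifies no week-level analysis.

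**3. Each variable against the schedule.**

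| Variable | Baseline value | Later value | Arms | As a baseline-adjusted outcome |
|---|---|---|---|---|
| Symptoms, quality of life | yes | yes | 1–4 | can be run |
| Emotional acceptance | Brief COPE | none described | 1–4 | cannot be run |
| Utilization | 5.5.1 yes, Table 3 no; period undefined | Visits 30, 90, 180 | 1–4 | can be an outcome; covariate undefined |
| Recording affect | Visit 0 | weekly | 1, 3 | can be run, arm 1 v arm 3 only |

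Standard MANCOVA uses only patients with every outcome present. On the documents supplied, the set containing acceptance therefore has 0 of 100 analysable patients. Without acceptance, quality of life remains analysable.

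**4. The recording-affect MANCOVA.** Two affect scores, an arm term and two baseline covariates in 50 patients leave 50 − 4 = 46 residual degrees of freedom. A trial fit on simulated data ran without difficulty. It estimates only the Fitbit contrast among active-app users. For one affect score, the difference detectable with 80% power (assumed two-sided 5%) is (1.960 + 0.842) × √(2/25) = 0.79 SD.

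**5. What the data could say about the link.** For one pair of values per patient, the detectable correlation at 80% power (assumed two-sided 5%) is tanh[(1.960 + 0.842)/√(n − 3)]:

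| n | detectable correlation |
|---|---|
| 50 | 0.39 |
| 40 | 0.43 |
| 30 | 0.49 |

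The rows for 40 and 30 show the effect of assumed attrition.

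Weekly data give more detail. 180/7 is 25 full weeks, and 25 × 50 = 1,250 possible recordings before any are missed. These are clustered in at most 50 patients and do not count as 1,250 independent observations. Table 3 and the Symptom Survey procedure in 5.5.1 supply in-app measures to pair with them: daily one-question ratings, weekly PF 6b, and PRO-CTCAE items spread over five days.

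**The case against.** The strongest reply is that the data needed for the aim are there. Arms 1 and 3 have baseline and weekly recordings, app measures, interviews and utilization, and linking recordings to outcomes needs only patients who have recordings. That stands, and it limits the point to the analysis plan.

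A reader might infer more, and the documents do not support it:

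- **That the MANCOVA cannot be run at all.** The symptom and quality-of-life outcomes can be run in all four arms, and recording affect in arm 1 v arm 3. Section 5.21n promises no four-arm or active-v-passive comparison of affect.
- **That utilization has no scheduled baseline.** Section 5.5.1 schedules the form at baseline. The defect is its conflict with Table 3 and the missing definition of the period covered.
- **That the MANCOVA contradicts 6.4**, where for unplanned infusions, emergency visits and hospitalizations "cumulative incidence functions will be calculated with death treated as a competing event". A different method in an exploratory analysis is not a contradiction, and utilization in 6.1 also includes phone calls. Nor do the 6.4 models contain a recording term, so pointing to them would not link recordings to utilization.
- **That acceptance is certainly never measured after baseline.** The interview forms (Appendices C and D) were not supplied, and FACIT-PAL is described only by domain and item count. The footnote to Table 1 says instruments changed after Phase 1, the section letters skip from 5.21f to 5.21j, and an acceptance scale remains in the reference list without a section of its own. A dropped instrument is plausible. That would explain the wording in 5.21n but would not make the outcome available.

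The reply that this analysis is neither a primary nor a secondary Phase 2 outcome in 6.1 is also correct, and it sets the severity.

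**Conclusion.** The point holds as a minor one. Followed as written, 5.21n compares groups on recording affect and on clinical outcomes separately and leaves the stated question unaddressed. The cause is the choice of method; the data could address it in up to 50 patients.

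Three smaller defects go with it:

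- Acceptance cannot serve as a baseline-adjusted outcome on the measures described.
- The reach of the recording analysis (at most 25 v 25, active-app users only) is not stated.
- The utilization baseline is undefined.

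This assumes full enrollment of 25 per arm, that Table 3 and 5.32a govern who receives the app surveys (5.21e gives different arm numbers for in-app symptom reports), and that no unsupplied form collects acceptance after baseline. Missed recordings and attrition would lower every count given here.

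**What to change.** Amend 5.21n as follows.

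1. Delete emotional acceptance as a MANCOVA outcome and keep the Brief COPE acceptance subscale as a baseline covariate or moderator. If a form does collect acceptance later, name it and its visits. If FACIT-PAL emotional well-being is used instead, say that it is a different construct.
2. Reconcile the chart-abstraction text in 5.5.1 with Table 3. Then either define the period that baseline utilization covers or drop the baseline adjustment for utilization.
3. Name the between-group factor, and state that recording analyses are limited to arms 1 and 3.
4. For the linking aim, add an exploratory mixed model on patient-weeks in arms 1 and 3. The outcomes are the in-app measures (PROMIS single items, PF 6b, PRO-CTCAE). The predictor is that week's LIWC positive or negative affect, split into the patient's mean and the deviation from it, with a patient random intercept. Define the pairing window in advance, because 5.21n lets a recording be made at any time until the next reminder.

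The cost is protocol wording and a modest amount of exploratory modelling, with no new data collection and no change to the EQ-5D analysis. Inference would be limited to at most 50 active-app users, and the write-up should say so.
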